4.6. Other Analyses

4.6.1. Risk factor analyses for selected outcome

If deemed necessary, logistic regression will be used for assessing association between selected risk factor(s) and selected pregnancy outcomes or AESIs (probability of event occurrence), statistically adjusting for potential confounding effects of other covariates.

CCI

4.6.2. Subgroup analyses

Subgroup analyses of preterm birth, neonatal death and other selected primary or secondary endpoints will be made to assess consistency of observed risk rate across different subgroups.

For the endpoints of preterm birth, it may be further broken down as: extremely preterm births (GA at birth: < 28 weeks); very preterm births (GA at birth: 28 - < 32 weeks); moderate to late preterm births (32 - < 37 weeks), if deemed necessary and data allow.

Subgroup analysis on safety summaries will be performed if deemed necessary.

CCI

4.6.2.1. Based on demographics, baseline and lifestyle characteristics

The following subgroups are planned to be examined:

- Age group at previous vaccination: 18-<35 years; \geq 35 years
- Age group at the time of deliver: 18-<35 years; \geq 35 years
- Pre-pregnancy BMI group: <30, \geq 30
- infant Sex: female vs male
- Prior preterm delivery
- Multiple gestation pregnancy
- RSV MAT-009 participants with preterm birth

- Retrospective or prospective cohort
- Gravidity

- CCI [REDACTED]
- [REDACTED]

If the number of participants is too small (less than [10%]) within a subgroup, then the subgroup categories may be redefined. Other selected demographics and lifestyle characteristics may also be included.

4.6.2.2. Based on prior parent studies

Subgroup analysis based on previous RSV MAT studies and other clinical studies participation will be performed.

Subgroup analysis for MAT-009 participants will specifically analyse separately among those with prior RSV MAT-009 participation, and among that subgroup by mothers who previously experienced: an infant with preterm birth in the prior study, infant with neonatal death in the prior study, and selected severe pregnancy outcome and AESIs.

4.6.2.3. Based on study cohorts

We plan to examine the primary and secondary endpoints by prior treatment arms while stratified by retrospective and prospective cohorts. If there is evident discrepancy for a primary/secondary endpoint between cohorts within a study arm, that endpoint will be further assessed regarding subject characteristics, medical history, concomitant medication and other risk factors. And a second analysis of primary and secondary objectives will be performed by stratifications of both prior treatment arms and cohorts.

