^a Any study contact may be via telephone, SMS, email, video-telephone/telemedicine or other means, depending on local best practice. If the study site is the participant's primary healthcare facility, contact with study personnel may also be made in the context of a visit for routine or event-driven care.

^b May be combined with another contact where pregnancy is first reported [e.g., combined with Visit 1/Contact 1 (for past/ongoing pregnancies at enrollment), follow-up contact, unscheduled contact.]

^c For participants who are not pregnant at 2 years post vaccine/control, the study conclusion will be completion of the last bi-annual contact, at least 2 months after 2 years post-vaccine/control. If the participant is pregnant at 2 years post vaccine/control **or at study enrollment**, study conclusion will be completion of Day 42 post-delivery. **WONCBP at study enrollment, or recipient of bilateral tube ligation prior to study enrollment will be excluded from the study if she has not conceived a pregnancy post-vaccine/control and does not plan to use any additional measures to attempt to conceive a pregnancy (e.g., sterilization reversal or in vitro fertilization (IVF)).**

^d Any SAEs assessed as related to study participation (e.g., protocol-mandated procedures) or related to a GSK product will be recorded from the time a participant consents to participate in the study.

Table 3 Schedule of Activities for prospective cohort – Infant participant

Type of contact ^a	Delivery ^b	Day 42 Contact ^b	Notes
Timepoints	Day 1	Day 42	
Informed consent	•		Infant informed consent is anticipated at delivery, but may be done at any time up to the delivery contact if allowed at the site (or at Visit 1/Contact 1 for an infant born from a past pregnancy)
Inclusion and exclusion criteria	•		
Demography and lifestyle characteristics	•	•	Demography at birth, and lifestyle at Day 42 post-delivery
Contact information for all HCPs seen by infant from birth through Day 42	○	○	
Safety assessments (from medical record review)			
Record medications/vaccinations	•	•	
Record medically attended AEs until Day 42	•	•	
Infant AESIs from birth until Day 42	•	•	
Infant SAEs from birth until Day 42	•	•	
Record SAEs related to study participation or related to a GSK product ^c	•	•	
MAEs, SAEs and AEs (AESIs) leading to study withdrawal	•	•	
Final Activities			
Study conclusion		•	

• Is used to indicate a study procedure that requires documentation in the individual eCRF.

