4.5. Study limitations

- The study participants who decide to enroll in this study are already aware whether they received RSVPreF3 or control. Study participants from prior RSV MAT pregnancy studies who experienced an adverse pregnancy outcome or a pregnancy/infant event from a prior pregnancy, may choose to participate in the current study at different rates than those who did not. This may lead to selection bias. As we have information on prior vaccination/control and prior adverse events/outcomes, we can evaluate whether this occurs and consider statistical analysis approaches to adjust for this.
- Comparison between incidence of events or outcomes in this study and events or outcomes in previous RSV MAT studies likely cannot be made directly because of the following possible limitations: 1) the expected sample size for this study is too small for the study to be adequately powered for comparisons, 2) this study has different inclusion and exclusion criteria, 3) this study has different timepoint of pregnancy at enrollment (as early as possible), and 4) different risk factors for participants in this study, such as a relatively short inter-pregnancy interval for pregnancies included in this study.
- This study includes two cohorts, one for which ***all*** data will be collected retrospectively and the other cohort for which data will be collected prospectively (***with some retrospective data collection***). This approach was taken so that the number of enrolled participants can be maximized. However, this may result in underestimation of the true incidence of AESIs in a pooled cohort (retrospective and prospective), as the retrospective cohort is more subject to recall bias.
- This study is conducted with a proportion of the same participants enrolled in previous RSV MAT studies which uncovered a safety signal, as described in Section 2.2. As there is still no plausible mode of action or known imbalance in risk factors across RSVPreF3 vs. control groups identified that explains the safety signal, the possibility remains there is unknown confounding (an unmeasured risk factor or exposure) leading to the safety signal. If there is unknown confounding, that may lead to a similar safety finding in this study.

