5. STUDY POPULATION

Prospective approval of protocol deviations to recruitment and enrollment criteria, also known as protocol waivers or exemptions, is not permitted.

The study population will include up to 8240 participants (***those who had conceived before study enrollment, those with ongoing pregnancy or who at enrollment may not have conceived but are followed for conception within 2 years post vaccine/control***) from RSV MAT studies to collect pregnancy outcome, pregnancy related AESIs and infant AESIs for any pregnancy conceived post-vaccination (***refer Section 9.5***).

All study participants who have received either RSVPreF3 vaccine or control (placebo, Tdap only, influenza vaccine only) will be included in this study.

Study participants with any pregnancy conceived after vaccination with Day 42 post-delivery at or before study start (i.e., any pregnancy conceived after vaccination is a past pregnancy) will be included in the retrospective cohort and retrospective data will be collected from medical records.

Study participants with any pregnancy conceived after vaccination ongoing at study start (pregnancy prior to Day 42 post-delivery) or newly reported during current study follow-up will be included in the prospective cohort and relevant data will be collected from medical records, as identified through structured follow-up contacts.

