5.1.2. Prospective cohort

Adult/Adolescent Participant:

- Adult/adolescent study participant from ***any of the prior RSV MAT*** studies who have either received RSV MAT vaccine or control (placebo, Tdap or influenza vaccine).
- Study participant:
 - Who has not reached 2 years+2 months post vaccine/control prior to/at enrollment or
 - Who has reached at least 2 years+2 months post vaccine/control but has an ongoing pregnancy (prior to Day 42 post-delivery) at enrollment. Participants who have reached 2 years post-vaccine/control before enrollment but are pregnant at enrollment will be enrolled and followed until Day 42 post-delivery for the pregnancy ongoing at enrollment.
- Female participants of childbearing potential.
- Provide signed and dated informed consent form.
- Be willing to comply with all study procedures and be available for the duration of the study.

Infant Participant:

- Participant live born as the result of a pregnancy followed in an adolescent/adult participant in this study.
- Participant's parent(s)/LAR(s), in the opinion of the investigator, can and will comply with the requirements of the protocol.
- Signed and dated informed consent form obtained from the participant's parent(s)/LAR(s) prior to performance of any study-specific procedure.

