8.4.5.2. Retrospective data source and data collection

For *pregnancies completed (through Day 42 post-delivery) prior to enrollment*, medical data related to pregnancy outcome, pregnancy related AESIs and infant AESIs of any pregnancy conceived post-RSVPreF3 or control vaccination, based on medical records, will be retrospectively collected. ***Data collection will be done through a single structured participant contact to retrospectively collect information about any healthcare received by the mother and infant during pregnancy up to Day 42 post-delivery. This will identify the medical records for review, so that information about any outcome, medically attended event, SAE, or event of special interest is obtained directly from medical records.***

All relevant data collected in the medical records will be recorded in an electronic case report form (eCRF).

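### Stratifying by enrolment cohort does not separate retrospectively from prospectively collected pregnancies, so any ascertainment contrast is diluted by an unknown amount

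*SAP*

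**What the plan says.** **The stratification.** SAP 4.6.2.3 states: "We plan to examine the primary and secondary endpoints by prior treatment arms while stratified by retrospective and prospective cohorts". SAP 4.6.2.1 also lists cohort among its subgroups. Further work follows under a condition with no numerical threshold: "If there is evident discrepancy for a primary/secondary endpoint between cohorts within a study arm".

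**The bias that is foreseen.** Protocol 4.5 expects that pooling the cohorts may understate AESI incidence, "as the retrospective cohort is more subject to recall bias". The same bullet acknowledges that the prospective cohort includes some retrospective collection.

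**How cohort is assigned.** Protocol 5.1.1 admits to the retrospective cohort women with a completed post-vaccination pregnancy who have reached 2 years + 2 months. Women of nonchildbearing potential or with bilateral tubal ligation may enter earlier. Protocol 5.1.2 opens the prospective cohort with "Who has not reached 2 years+2 months post vaccine/control prior to/at enrollment or", the alternative being an ongoing pregnancy. It does not exclude a woman whose pregnancy is already complete.

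**How collection mode is assigned.** This goes by pregnancy. Protocol 8.4.5.2 applies look-back collection to "pregnancies completed (through Day 42 post-delivery) prior to enrollment". Protocol 8.4.5.3 applies repeated contacts to pregnancies ongoing at enrolment or conceived later. The prospective schedule expects both kinds: footnote b of Protocol Table 2 allows the pregnancy contacts to be "combined with Visit 1/Contact 1 (for past/ongoing pregnancies at enrollment"), and Table 3 provides for infants already past Day 42 when the mother enrols.

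**A different assignment rule.** Protocol Section 5 begins its description of the retrospective cohort with "Study participants with any pregnancy conceived after vaccination with Day 42 post-delivery at or before study start" and does not mention time since vaccination.

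**The concern.** A reader will naturally use the cohort split to judge whether retrospective collection lost events, and will treat the prospective estimate as the cleaner one. The split cannot carry that reading. A woman less than 2 years + 2 months from vaccination whose pregnancy is over counts as prospective, although her data are gathered by looking back. Her presence pulls the two cohort rates together, so a discrepancy is less likely to look evident even if under-ascertainment is real, and the prospective figure keeps some of the same loss.

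The Section 5 wording adds a practical risk. Protocol 4.1 and 4.4 end the study period at enrolment for the retrospective cohort, but continue it to 2 years + 2 months, or to Day 42 after delivery, for the prospective cohort. For a woman still inside the window, the choice of text decides whether a later pregnancy is followed, and that bears on the any-pregnancy secondary endpoint.

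**Working it through.** **1. Scale of the study.** Protocol 9.5 expects about 650 participants with a pregnancy. Check: 2540 × 0.10 × 0.60 = 152.4, and 5700 × 0.50 × 0.30 × 0.60 = 513.0. The sum is 665.4, consistent with the rounded 150 + 500.

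**2. The dilution.** Let p be the true event rate, s the share of events captured by look-back collection, and f the look-back share of the prospective cohort's pregnancies. Assume the same p in both cohorts, full capture in prospective collection, and a retrospective cohort that is wholly look-back, as Protocol 4.5 describes it.

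- Retrospective cohort rate: p·s
- Prospective cohort rate: p·(1 − f + f·s)
- Difference: p·(1 − s)·(1 − f)

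The documents supply a reference for p only: 5%, the lowest rate of the safety signal in a MAT-009 group (Protocol 9.5). Both s and f are assumptions, so a range is shown. Difference between cohorts, in percentage points, at p = 5%:

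| s | f = 0 | f = 0.10 | f = 0.25 | f = 0.50 | f = 0.66 |
|---|---|---|---|---|---|
| 0.9 | 0.50 | 0.45 | 0.38 | 0.25 | 0.17 |
| 0.7 | 1.50 | 1.35 | 1.13 | 0.75 | 0.51 |
| 0.5 | 2.50 | 2.25 | 1.88 | 1.25 | 0.85 |

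For s = 0.7 and f = 0.5, the cohort rates are 3.50% and 5 × (0.5 + 0.5 × 0.7) = 4.25%.

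**3. What f could be.** Vaccination stopped on 28 February 2022 (Protocol 2.2) and the assumed start is 7 December 2022 (Protocol 9.5), which is 282 days later. The cohort cut-off is 790 days (Protocol Table 4), and 7 December 2022 minus 790 days is 8 October 2020. Women vaccinated after that date are prospective at the assumed start, apart from the 5.1.1 exception for nonchildbearing potential or tubal ligation.

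Assume conceptions spread evenly over 730 days, and a pregnancy lasting L days from conception plus 42 days. The share already complete at enrolment on day t after vaccination is (t − L − 42)/730, with a floor of zero.

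| Enrolment day t | Term, L = 266 | Early loss, L = 56 |
|---|---|---|
| 282 | 0% | 184/730 = 25% |
| 365 | 57/730 = 8% | 267/730 = 37% |
| 548 | 240/730 = 33% | 450/730 = 62% |
| 730 | 422/730 = 58% | 632/730 = 87% |
| 789 | 481/730 = 66% | 691/730 = 95% |

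If t is uniform over 282 to 789, the means are 31% and 60%. Women vaccinated while pregnant, about 500 of the 650, would have a lower f, because that pregnancy must end first.

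**4. Sensitivity of the comparison.** With 325 pregnancies per cohort (an assumed even split of 650), p = 5%, s = 0.7 and two-sided 0.05, power is 15.6% at f = 0, 10.9% at f = 0.25 and 7.1% at f = 0.50. At f = 0, 80% power would need 2838 per cohort.

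**5. Which flag to use.** Protocol 8.4.5.2 and 8.4.5.3 suggest flagging by whether Day 42 had passed at enrolment. That depends on when the pregnancy ended, and so on its outcome. Take enrolment at day 548, even conception and perfect capture.

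- Loss at day 56, true rate 15%. Retrospective group: 0.15 × 0.616 / (0.15 × 0.616 + 0.85 × 0.329) = 25%. Prospective group: 0.15 × 0.384 / (0.15 × 0.384 + 0.85 × 0.671) = 9%.
- Birth five weeks early (L = 231), true rate 5%. Share complete: (548 − 231 − 42)/730 = 37.7%. Retrospective group: 0.05 × 0.377 / (0.05 × 0.377 + 0.95 × 0.329) = 5.7%. Prospective group: 0.05 × 0.623 / (0.05 × 0.623 + 0.95 × 0.671) = 4.7%.

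These contrasts arise with no ascertainment bias at all, and they run opposite to under-reporting.

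**The case against.** **Purpose.** SAP 4.6.2.3 never calls itself a check on under-reporting. Its follow-up to a discrepancy looks at participant characteristics, history, medication and risk factors, and the cohorts differ in time since vaccination, which is a fair reason to stratify. This stands. The link to ascertainment comes from Protocol 4.5, so a reader who infers that the SAP set up a bias test and got it wrong goes further than the text. It is also the reason to keep the cohort stratification.

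**Disclosure and data source.** Protocol 4.5 openly says that the prospective cohort has some retrospective data. On both routes the participant contact identifies records and the outcomes are taken from them; SAP 4.2.2 counts only record-based pregnancies, and Protocol 8.3.1 provides blinded adjudication of preterm births. This stands too. Any loss would act mainly through pregnancies or providers that the woman does not recall, and may be small. Disclosure does not make cohort a measure of collection mode.

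**Size.** It is tempting to read 282/730 = 39% as the look-back share, or to say that the contrast is halved. Neither is supported. The 39% is elapsed window: at day 282 no term pregnancy can have reached Day 42, since 266 + 42 = 308 days. Halving requires f = 0.5, which the documents do not give.

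**Power and redaction.** The comparison is insensitive even undiluted, and redacted text in SAP 4.2.2, 4.2.3, 4.3.1.2, 4.6.1, 4.6.2 and 4.6.2.1 could hold an analysis by collection mode. Both stand, so the point is confined to the visible text.

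**Section 5.** The inclusion criteria are specific and waivers are barred, so a site that follows 5.1 would not end follow-up early. That lowers the risk; the two texts still disagree.

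**Conclusion.** The point holds in a limited form. The visible stratification by enrolment cohort mixes collection modes. If look-back collection under-ascertains events, the contrast between cohorts is reduced by the factor (1−f). The direction follows from the Protocol's own definitions, given equal true rates in the two cohorts. The size is unknown, because f and s are not in the documents, and it may be modest. Early losses would be the most exposed, since they are more often complete at enrolment.

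A reader might also infer that the RSVPreF3-versus-control comparison is biased by this. Nothing here shows that: the dilution concerns the comparison between cohorts within an arm. Nor would a correct classification make the comparison sensitive, with power of about 16% at s = 0.7 and no dilution.

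The conflict between Protocol Section 5 and 5.1.1/5.1.2 does not depend on any of these assumptions.

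**What to change.** 1. Keep the cohort stratification in SAP 4.6.2.1 and 4.6.2.3. Add to 4.6.2.3 a supplementary pregnancy-level analysis by collection mode, within study arm.
2. Base the flag on conception date relative to enrolment, not on when the pregnancy ended. For example: (a) conceived about 308 days or more before enrolment, so that a term pregnancy would have passed Day 42: wholly look-back; (b) conceived after enrolment: wholly prospective; (c) in between: mixed.
3. Present it as descriptive and state its low power. Note that groups (a) and (b) may still differ in time since vaccination, so a difference between them would not by itself prove under-ascertainment.
4. Reconcile Protocol Section 5 with 5.1.1 and 5.1.2, so that a woman inside 2 years + 2 months with a past pregnancy has one stated cohort and one stated end of follow-up.

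Cost: one derived variable, one extra table and a wording clarification. No new data should be needed, since SAP 6.2.2 already uses the conception date as its safety reference date.

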4.7. Interim Analyses

Not applicable.

4.8. Changes to Protocol Defined Analyses

CCI [REDACTED], this is an addition to the originally planned statistical analysis specified in the Protocol Amendment 2 (Dated: 21-JUN-2023).

5. SAMPLE SIZE DETERMINATION

All analyses will be descriptive and thus no hypothesis driven sample size calculation was conducted.

All study participants (approximately 8240) from prior RSV MAT studies will be considered for enrolment in this study based on the eligibility criteria. Assuming the study will start on December 7th, 2022, the study potential subjects include: (1) those who had deliveries defined in the Protocol Section 5.1.1 (to be enrolled to Retrospective cohort); (2) those with ongoing pregnancy, or who at enrolment have not conceived but subsequently conceive within two years since the vaccination/control in previous RSV MAT studies (to be enrolled to Prospective cohort). The actual sample size will mainly depend on: (1) the enrolment rate of those subjects who participated in the previous RSV MAT studies; (2) the incidence rate of pregnancy conceived post RSVPreF3 (or control) vaccination during study period.

To estimate the incidence rate of first pregnancy conceived post RSVPreF3 (or control) vaccination, we considered the likelihood of pregnancy among participants in prior studies of non-pregnant women and pregnant women separately (approximately 8240 total). Among non-pregnant women (approximately 2540), we estimate approximately 10% will have a pregnancy during the time period of this study [Curtin, 2013]. Assuming 60% enroll in this study, we estimate approximately 150 non-pregnant women in prior studies who enroll in this study will have a pregnancy. Among pregnant women (approximately 5700), we estimated approximately 50% would have another pregnancy. From data on inter-pregnancy intervals in US women, we estimated approximately 30% of those subsequent pregnancies will occur during the time period of this study [Thoma, 2016]. Assuming 60% enroll in this study, we estimate approximately 500 non-pregnant women in prior studies who enroll in this study will have a pregnancy. In total, we estimate approximately 650 enrolled study participants will have at least one pregnancy of interest for this study and contribute to the total number of pregnancies from which incidence rates for events will be calculated.

The lowest rate of the safety signal observed in a MAT-009 study group was approximately 5%. A sample size of 300 pregnancy participants will provide 100% probability to detect at least one event (e.g., preterm birth event), providing the true rate is 5%. Assuming only 100 of 300 pregnancy participants are from the previous RSVPreF3 group, it can provide 99.4% probability to detect at least one event on the condition of the true event rate at 5%. For a sample size of 300 pregnancy participants, it will still provide a probability of 78%, 95% or 99% to observe at least one participant with event of interest, even if the true event rate is as low as 0.5%, 1% or 1.5%, respectively. A sample size of 650 pregnancy participants will provide a probability of 96% or 100% to observe at least one participant with event of interest, even if the true event rate is as low as 0.5% or 1%, respectively. The Table 4 presents more scenarios of sample size consideration regarding event rates.

Table 4 Sample size, event rate and probability

| Sample size | Event Rate | Probability to observe at least one event |
|-------------|------------|---|
| 300 | 0.5% | 78% |
| | 1% | 95% |
| | 1.5% | 99% |
| | 3% | 100% |
| | 5% | 100% |
| | 7% | 100% |
| 500 | 0.5% | 92% |
| | 1% | 99% |
| | 1.5% | 100% |
| | 3% | 100% |
| | 5% | 100% |
| | 7% | 100% |
| 650 | 0.5% | 96% |
| | 1% | 100% |
| | 1.5% | 100% |
| | 3% | 100% |
| | 5% | 100% |
| | 7% | 100% |
| 1000 | 0.5% | 99% |
| | 1% | 100% |
| | 1.5% | 100% |
| | 3% | 100% |
| | 5% | 100% |
| | 7% | 100% |

In consideration of the precision of 95% Clopper-Pearson confidence interval (CI) for the event rate, if observed 5% participants experienced a pregnancy outcome AESI among 300 participants, the two-sided 95% CI would be within (2.8%, 8.1%). And among 650 participants, the two-sided 95% CI would be within (3.5%, 7%). The [Table 5](#) presents the precision one can get in more scenarios. Even approximately 300 participants with pregnancy information are included in the study would still provide reasonable precision to detect and estimate most of the events of interest in the study.

Table 5 95% CI on the percentage of participants with event(s) of interest

| Sample size | Number of Event(s) | % of Event | 95% CI | |
|-------------|--------------------|------------|-------------|-------------|
| | | | Lower Limit | Upper Limit |
| 300 | 1 | 0.33 | 0.0 | 1.8 |
| | 3 | 1 | 0.2 | 2.9 |
| | 5 | 1.67 | 0.5 | 3.8 |
| | 9 | 3 | 1.4 | 5.6 |
| | 15 | 5 | 2.8 | 8.1 |
| | 21 | 7 | 4.4 | 10.5 |
| | 30 | 10 | 6.8 | 14.0 |
| 500 | 1 | 0.2 | 0.0 | 1.1 |
| | 5 | 1 | 0.3 | 2.3 |
| | 10 | 2 | 1.0 | 3.6 |
| | 15 | 3 | 1.7 | 4.9 |
| | 25 | 5 | 3.3 | 7.3 |
| | 35 | 7 | 4.9 | 9.6 |
| | 50 | 10 | 7.5 | 13.0 |
| 650 | 1 | 0.15 | 0.0 | 0.9 |
| | 7 | 1 | 0.4 | 2.1 |
| | 10 | 1.5 | 0.7 | 2.8 |
| | 20 | 3 | 1.8 | 4.6 |
| | 33 | 5 | 3.5 | 7.0 |
| | 46 | 7 | 5.2 | 9.2 |
| | 65 | 10 | 7.8 | 12.6 |
| 1000 | 5 | 0.5 | 0.2 | 1.2 |
| | 10 | 1 | 0.5 | 1.8 |
| | 15 | 1.5 | 0.8 | 2.5 |
| | 30 | 3 | 2.0 | 4.3 |
| | 50 | 5 | 3.7 | 6.5 |
| | 70 | 7 | 5.5 | 8.8 |
| | 100 | 10 | 8.2 | 12.0 |

Note: Precision estimation using PASS2019 19.0.1 (Clopper-Pearson Confidence Intervals for One Proportion).

